### **1.2 Secondary Objectives**

The secondary objectives of TACT2 are to determine:

1. if the chelation-based strategy reduces the overall rate of occurrence of the events which define the primary TACT2 endpoint: all-cause mortality, myocardial infarction, stroke, coronary revascularization, or hospitalization for unstable angina events compared to placebo chelation strategy.
2. if the chelation-based strategy increases the time to the first occurrence of a combined secondary endpoint: cardiovascular mortality, myocardial infarction, or stroke compared to placebo chelation strategy.
3. if the chelation-based strategy increases the time to all-cause mortality compared to placebo chelation strategy.

Exploratory analyses, defined as those seeking to confirm a signal of benefit observed in TACT, or to develop mechanistic hypotheses for benefits of chelation expected in TACT2, include:

- i. Analysis of the primary endpoint in patients receiving OMVM compared with oral placebo
- ii. Analysis of the primary endpoint in patients receiving active chelation + active OMVM, compared with placebo chelation + placebo OMVM
- iii. Analysis of markers of severity of diabetes (fasting glucose, HbA1c, microalbuminuria) throughout the infusion regimen
- iv. Analyses of lead and cadmium in blood and urine to:
  - a. Compare the change in metal internal dose (blood lead and urine cadmium) in TACT2 participants, from infusion 1 to infusion 40 (or 1 year) in the active versus placebo infusion arms.
  - b. Evaluate whether higher screening metal internal dose (blood lead and urine cadmium) and the extent of depletion of those stores identify patients more likely to benefit from chelation.
- v. Collection of biospecimens for the constitution of a biorepository to support future

mechanistic work. Samples of blood (plasma and buffy coat) and urine will be stored at -80°C in a secured biorepository to ensure their availability for the evaluation of future hypotheses that will be guided by the results of the trial.

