### Preliminary data on metal excretion following a TACT2 infusion

A preliminary study measured metal excretion after one infusion of placebo, and one of active chelation. Twenty male participants (mean age 66, range 51 to 81) were recruited using the same criteria as in TACT (post-MI, age  $\geq 50$ , creatinine  $\leq 2.0$  mg/dL). Urinary concentrations of 20 toxic metals (Al, Sb, As, Ba, Be, Bi, Cd, Cs, Gd, Hg, Pb, Ni, Pd, Pt, Te, Tl, Th, Sn, W, U) normalized to creatinine excretion were measured at baseline, for 6 hours following a placebo infusion of 500 mL normal saline and 1.2% dextrose, and for 6 hours following a 3 gram edetate disodium-based infusion as used in TACT.

Following an edetate disodium-based TACT infusion, there was a striking increase in the urinary excretion of lead (mean 3,926% increase,  $P < 0.001$ ; Figure A), cadmium (739% increase,  $P < 0.001$ ; Figure B), and nickel (131% increase,  $P < 0.001$ ). There was also a modest increase in the urinary excretion of tin and thallium (30-40%;  $P < 0.05$ ). These preliminary data show that

Effect of Placebo or Edetate disodium-based infusion on urinary lead (A) and cadmium (B) excretion\*

\*Lines represent individual patient data points. Bar graphs are mean  $\pm$  SD of % change from baseline.

an edetate disodium-based infusion, identical to that used in TACT and proposed for TACT2, markedly increased excretion of lead and cadmium. Whether enhanced excretion of metals following repeated chelation infusions leads to a reduction in blood lead or pre-infusion urine cadmium (reflecting total body stores of each) is unknown, but will be identified by TACT2.

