### **Randomization and scheduling first infusion**

A simple randomization scheme reflecting an equal allocation ratio to the four different treatment groups (1 active chelation / active OMVM: 1 active chelation / placebo OMVM: 1 placebo chelation / active OMVM: 1 placebo chelation / placebo OMVM) will maximize the power for detecting treatment differences at the time of the interim and final analyses.

Patients who are confirmed eligible to participate in TACT2 will be notified by the site study personnel. The patient will be randomly assigned to a blinded treatment group by the EDC system (this is the randomization date), and the first infusion visit will be scheduled. The allowable range of time during which all screening activity (defined by date of consent) must be completed is 30 days. After 30 days, if randomization has not taken place, screening labs must be re-drawn. The first infusion, should occur within 2 weeks of randomization.

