#### **6.2.3 Subsequent Infusion Visits (2-40)**

The detailed schedule and activities of the follow-up visits are covered in Section 6.1 (Table 2). Within the infusion period in Year 1, most visits are associated with an infusion number, and do not have a traditional time-window for performance.

During the infusion year, the only time-dependent visit landmarks in TACT2 are:

1. The first infusion, which should occur within 2 weeks of randomization.
2. In non-adherent patients who have stopped receiving infusions, safety labs will not be checked. However, the study site will make all possible efforts to bring these patients in for blood and urine metal collection as well as scheduled fasting glucose, HbA1c, and microalbumin. During these specimen visits, patients will also complete a clinical visit including history, and a brief exam. Subjects no longer receiving infusions are expected to return at week 5, 20, and 40 post-randomization for these visits. For patients who have stopped receiving infusions, a urine / blood sample within 4 months of the last infusion is informative regarding their metal levels at the time the patient stopped infusions. The CCC should be consulted for all non-adherent patients. The management of the non-adherent patient will be covered in detail in the MOP.

The data collected in each call is covered in the Table in Section 6.1.

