### **Exploratory Endpoints**

The comparison of costs will test mean direct medical costs incurred during the study (index infusion through end of follow-up). To account for staggered entry and incomplete follow-up, costs will be adjusted using the approach of Bang and Tsiatis. Statistical comparisons will be made using a normal approximation with standard errors

estimated using the bootstrap approach. The probability of differences in cost greater than thresholds of policy interest (such as \$1000, \$2000, or \$5000) will be calculated. Differences in cost by treatment group will be interpreted in the context of the trial clinical results, looking for both consistency and plausibility. Follow-up costs will be presented both overall and by category (e.g., inpatient readmission, outpatient procedures, concomitant medications, non-acute institutional care). Cumulative costs over the study period between treatment groups will be compared. Descriptive comparisons of cost according to clinical variables defining subgroups of interest will also be performed.

The analyses for toxic metals in blood and urine in the TACT2 population will proceed in three phases. First, we will evaluate if the chelation regimen has the effect on metal internal dose that we have postulated. To do this, we will compare body metal levels (lead in blood, pre-chelation urine lead and cadmium, and post-chelation urine lead and cadmium, in separate analyses) between active and placebo chelation groups at baseline and over the treatment phase of TACT2. Second, we will relate those levels to changes in the primary clinical endpoint (a composite of death from any cause, recurrent MI, stroke, coronary revascularization, or hospitalization for unstable angina) caused by chelation therapy relative to placebo. Finally, we will perform the exploratory analyses described below.

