Over the 1-year period, we hypothesize there will be no change in metal levels in the placebo chelation group and significant reductions in the active chelation group. We also postulate these patterns of change in metal levels will explain, in a statistical sense, the clinical benefits we expect to see in TACT2 (the way LDL-cholesterol level lowering “explains” the benefits of statin therapy) using three complementary analytic approaches: 1] prespecified subgroup analyses (patients in the highest tertile of blood lead, urine cadmium, and post-chelation urine lead and cadmium at infusion 1, will show significantly larger treatment benefits (chelation vs. placebo) than patients with lower baseline levels), 2] landmark analyses (patients in the chelation arm with lower metal levels after 40 infusions/1 year of chelation will show significantly larger clinical benefits than patients with higher levels), and 3] we will apply causal inference modeling to evaluate whether the pattern of metal changes (lead in blood and cadmium in urine) in the chelation arm over the treatment period of TACT2 statistically “explains” the variation in clinical outcomes responsible for the hypothesized superiority of the chelation strategy.

We will also do exploratory analyses to examine the clinical implications of different patterns of metal removal over time on the benefits of chelation therapy (can metal levels be used as a biomarker to guide the number of chelation sessions needed to maximize clinical benefit from this therapy?) and to examine the effects of the oral multivitamin/mineral treatment regimen versus placebo vitamins on metal levels and on the effectiveness of chelation in reducing those levels (does the TACT2 vitamin regimen augment the ability of the chelation regimen to remove metals, or might there be a different mechanism of action altogether?). The latter case could be inferred if there were clinical benefits of OMVM, but no changes in lead and cadmium levels.

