## **Subgroup Analyses**

To examine the heterogeneity of the treatment effect, subgroup analyses for the primary and secondary endpoints will be performed in order to explore whether the treatment effect is consistent across subgroups. Subgroup analyses to evaluate variation in the effect of treatments will be performed using interaction terms within the Cox proportional hazards model. For binary variables, we will include the subgroup factor as a stratification variable within the Cox regression model. This model structure will decrease the reliance on the proportional hazards assumption. Additionally, treatment effects within each categorical subgroup will be examined separately using Cox proportional hazards models. Event rates by treatment and HRs with 95% confidence intervals will be reported for each subgroup. Forest plots will be generated displaying the estimated hazard ratios and 95% confidence intervals for each subgroup. For subgroups defined using continuous variables, the analysis based on the continuous form will be considered primary but for display purposes these variables can also be categorized.

We have pre-specified sex, minorities, age greater than 70, myocardial infarction location (anterior MI or not), type of diabetes (1 or 2), insulin treatment of diabetes, use of statin therapy at baseline (for the OMVM analyses only), known peripheral artery disease at baseline as key subgroups of interest. There are also pre-specified analyses by tertiles of lead and cadmium as indicated above. The examination of these pre-specified subgroups will include formal tests of interaction within the Cox regression model.

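### Exploratory metals analysis: post-chelation urine lead and cadmium at infusion 1 are used as baseline subgroup factors for chelation versus placebo, although they are measured after randomization and changed by the active infusion

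*Protocol*

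**What the plan says.** The metals part of Protocol 9.6 (Exploratory Endpoints) offers three ways to show that metal changes account for the clinical effect. The first is a set of prespecified subgroups, in which the high-burden group is defined as "patients in the highest tertile of blood lead, urine cadmium, and post-chelation urine lead and cadmium at infusion 1". The stated prediction for this group is that its members "will show significantly larger treatment benefits (chelation vs. placebo) than patients with lower baseline levels". The Subgroup Analyses text of 9.6 confirms that the lead and cadmium tertile analyses are pre-specified and brings them under formal interaction testing. It adds: "For subgroups defined using continuous variables, the analysis based on the continuous form will be considered primary".

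The timing is clear. Under Randomization and scheduling first infusion (Protocol 6.2.1): "The patient will be randomly assigned to a blinded treatment group by the EDC system (this is the randomization date". Protocol 6.2.3 gives the next step: "The first infusion, which should occur within 2 weeks of randomization". The Schedule of Evaluations (6.1) and the biorepository text (6.1.2) place metal samples at infusions 1, 5, 20 and 40, with none at screening.

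The Protocol also treats the same measure as something chelation may change. To see whether the regimen acts on metals as postulated, 9.6 says "we will compare body metal levels (lead in blood, pre-chelation urine lead and cadmium, and post-chelation urine lead and cadmium, in separate analyses" across the two arms. In the pilot (Protocol 2.2), after one active infusion "there was a striking increase in the urinary excretion of lead (mean 3,926% increase"; the cadmium rise was 739%.

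Other places are narrower. Exploratory objective iv.b in Protocol 1.2 reads "Evaluate whether higher screening metal internal dose (blood lead and urine cadmium) and the extent of depletion of those stores", with no post-chelation measure. SAP 3.4 lists tertiles of blood lead and urine cadmium only, without saying pre- or post-infusion. SAP 2.5 refers pre- and post-chelation metals to a separate SAP that is not among the documents.

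**The concern.** A subgroup factor for a randomized comparison should be one that treatment cannot have altered. Then each level contains comparable active and placebo patients, and a difference in effect between levels can be read as effect modification. Urine metal collected after infusion 1 fails this condition because assignment itself shifts it, and by a large factor in the pilot.

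The Protocol does not state the cut-point rule, and each choice causes a different problem:

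- **Common cut-points.** The tertile comes close to identifying the arm, so the top tertile has few placebo patients to compare with.
- **Arm-specific cut-points.** Counts are balanced, but high means much chelatable metal on active and much spontaneous excretion on placebo. Whether those are the same kind of patient is an assumption that randomization does not supply.

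At stake is the reading of one pre-specified analysis meant to support the metal-removal mechanism.

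**Working it through.** The plan states no figure for this analysis, so there is none to reproduce. The check asks how far the subgroup departs from a randomized contrast.

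**Inputs from the documents.** 1000 patients, about 500 per chelation arm (Protocol 9.2); 282 primary events (SAP 1.1); mean folds from the pilot of 1 + 39.26 = 40.26 (lead) and 1 + 7.39 = 8.39 (cadmium).

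**Assumptions.** Log-normal pre-infusion urine metal with log SD σ = 0.5-1.1; log SD of the individual response to the active infusion τ = 0-1.0; no change on placebo; no treatment effect on events; a hazard ratio (HR) per SD of pre-infusion log metal (the burden HR) of 1.0, 1.1 or 1.2. None of these is in the supplied text.

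**Step 1: common cut-points, who is in the top tertile.** Let m = ln(fold) − τ²/2, which keeps the mean fold at the pilot value. The upper cut-point t solves

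½[1 − Φ(t/σ)] + ½[1 − Φ((t − m)/√(σ² + τ²))] = 1/3,

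and the placebo share of the top tertile is 3 × ½[1 − Φ(t/σ)]. At the least separated corner (σ = 1.1, τ = 1.0), m = 3.695 − 0.5 = 3.195 for lead, giving 1.4%. For cadmium m = 2.127 − 0.5 = 1.627, giving 15.5%. Over the whole grid:

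| Fold used | Lead, placebo share | Cadmium, placebo share |
|---|---|---|
| Pilot | 0-1.4% | 0-15.5% |
| Half of pilot | 0-5.2% | 1.1-27.4% |
| Quarter of pilot | 0-12.8% | 14.4-41.4% |

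A true baseline factor gives about 50%. At σ = 1.5 with the pilot folds, the shares are 2.8-6.2% and 15.6-22.6%. None of this depends on a burden HR.

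**Step 2: events available.** Expected placebo events in the top tertile are at most about 0.014 × 333 × 0.282 = 1.3 for lead and 0.155 × 333 × 0.282 = 14.6 for cadmium. A true baseline factor would have 0.5 × 333 × 0.282 = 47. In simulated trials, 27-100% (lead) and 0-99% (cadmium) had no placebo event in that tertile.

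**Step 3: common cut-points, false effect under the null.** In the middle tertile, where both arms are present, the active patients are those with low pre-infusion metal and the placebo patients those with high. At burden HR 1.0 / 1.1 / 1.2 the false rate ratio is 1.00 / 0.81-0.86 / 0.67-0.76 (lead) and 1.00 / 0.81-0.91 / 0.67-0.84 (cadmium).

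**Step 4: arm-specific cut-points under the null.** The top-tertile ratio is 1.00 / 0.95-1.00 / 0.90-1.00 and the bottom-tertile ratio 1.00 / 1.00-1.06 / 1.00-1.13. With τ = 0 the post-infusion ranks within the active arm equal the pre-infusion ranks, and the ratio is exactly 1.00. These figures assume that response to the infusion is itself unrelated to prognosis.

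**Step 5: continuous form.** A Cox model with arm, log post-infusion metal and their product was fitted to 1000 null trials in each of five (σ, τ) settings. The interaction was significant at 0.05 in about 4-6% / 4-9% / 6-17% of trials at burden HR 1.0 / 1.1 / 1.2, both metals together (Monte Carlo SE about 0.6-1.2 points).

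**The case against.** The strongest case on the other side has five parts.

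1. **The continuous form is primary.** Step 5 shows it near nominal at burden HR 1.0 and only modestly inflated at 1.1. This stands, and it limits the harm. It does not remove the point: the hypothesis is worded by tertile, the tertile analyses are pre-specified, and the continuous form does not cure the different meaning of the factor in each arm.

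2. **Arm-specific tertiles leave little bias.** This also stands. A reader might infer that the analysis can never test whether patients with a higher metal burden gain more. The documents do not support that: with arm-specific cut-points and a uniform response, it reduces to the pre-infusion tertiles. Validity depends on a cut-point rule and a response spread that the supplied text does not give.

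3. **The folds may not transfer.** They come from 20 men, 6-hour creatinine-normalized collections and a 3 g infusion, whereas TACT2 infusions contain up to 3 g and collection details are left to the manual. At a quarter of the pilot fold, the cadmium top tertile would be estimable. The pilot figure that may show the spread is not reproduced in the supplied text, so its absence here is no fault of the plan.

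4. **It may already be settled.** SAP 3.4 names no post-chelation factor, and the separate metals SAP may handle the matter. A reader might infer that the flawed version is the operative analysis; that cannot be established. But SAP 3.4 covers the primary manuscript and does not withdraw the Protocol text.

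5. **All infusion-1 metals follow randomization.** A reader might extend the criticism to blood lead and urine cadmium. Drawn before the infusion, they cannot have been changed by it and remain valid baseline factors.

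**Conclusion.** The point holds as a minor one, confined to the exploratory metals analyses. The Protocol pre-specifies a chelation-versus-placebo subgroup on a variable measured after randomization and shifted by the active infusion, calls it baseline, and leaves the cut-points open.

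Its size depends on how the gap is filled. Common cut-points would largely turn tertile into arm for lead, and for cadmium to a degree that depends on the actual rise. Arm-specific cut-points give small or no numerical bias under the assumptions tested, but need a comparability assumption that has to be stated. The continuous form shows material false positives only toward burden HR 1.2 with varying response. If burden is not prognostic, there is no false effect in any form. The imbalance under common cut-points needs no burden HR, but it does rest on the pilot folds and the assumed spreads.

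Nothing here touches the primary, secondary or safety inferences.

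**What to change.** In Protocol 9.6, define the chelation-versus-placebo metal subgroups on blood lead and urine cadmium drawn before infusion 1, with cut-points common to both arms, and remove post-chelation urine lead and cadmium from that list. Use post-infusion values as metal-removal outcomes, as 9.6 already plans, or as prognostic markers within an arm. If a chelation-versus-placebo analysis by post-infusion level is still wanted, label it post-randomization and non-randomized, and state its cut-points and causal assumptions.

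Three other texts need matching:

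- The closing paragraph of Protocol 1.2, which plans post-infusion urine metals as predictors of benefit from chelation. A within-arm marker cannot show that.
- Objective iv.b, which speaks of screening levels although metals are first drawn at infusion 1.
- The separate metals SAP.

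The cost is wording only, since pre- and post-infusion samples are already in the Schedule of Evaluations. The real loss is that chelatable burden can no longer be presented as a randomized effect-modifier hypothesis.

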### Possible Benefit of Chelation Therapy

The epidemiologic evidence that many metals are toxic and promote cardiovascular disease is robust, particularly for lead and cadmium, metals chelated by the edetates. One possible hypothesis, which is an exploratory analysis within the present trial, is that edetate disodium-based chelation depletes body stores of ubiquitous toxic metal pollutants, lead and cadmium in particular, acquired from the environment over many years and that depletion of toxicants leads to improved outcomes.

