### Infusion Schedule

Infusions will be administered on a weekly basis for 40 weeks through a peripheral intravenous line over at least 3 hours. Due to vacations, travels, weather, and illness,

the infusion regimen can be extended but is expected to be completed by 1 year. Clinical sites, however, will be instructed that if a patient has not completed the infusions by 1 year, they should continue trying to get the patient to clinic until the 40th infusion is complete. The total number of infusions is key, not the weekly schedule on 1-year completion. **The overall goal of the treatment schedule is to deliver all 40 infusions; no matter how long it takes.** The DCRI Call Center will follow patients for clinical events, but not for infusion scheduling or other site-centered events beginning 6 and 12 months after randomization, and at 4 month intervals subsequently until the study ends.

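### The metals landmark analysis groups chelation-arm patients by attained metal level, with no placebo contrast or baseline adjustment, so it estimates prognosis, not benefit from chelation

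*Protocol*

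**What the plan says.** Protocol section 1.2, exploratory item iv.b, asks whether a higher screening metal level and "the extent of depletion of those stores identify patients more likely to benefit from chelation".

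Section 9.6, Exploratory Endpoints, offers three complementary approaches to showing that metal change explains the clinical result:

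- **Approach 1** groups patients by infusion-1 level and names the randomised contrast. Those in the highest tertile "will show significantly larger treatment benefits (chelation vs. placebo) than patients with lower baseline levels".
- **Approach 2** is the landmark analysis: "landmark analyses (patients in the chelation arm with lower metal levels after 40 infusions/1 year of chelation will show significantly larger clinical benefits" than those with higher levels. It names no placebo group, no adjustment for starting level, no cut-point and no fixed landmark day.
- **Approach 3** is causal inference modelling of the metal changes, not specified further.

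Earlier in the same section the protocol says "we will relate those levels to changes in the primary clinical endpoint" that chelation causes relative to placebo. It does not say how approach 2 would do this. Section 2.2 gives the premise: "The epidemiologic evidence that many metals are toxic and promote cardiovascular disease is robust, particularly for lead and cadmium".

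SAP section 2.5 refers pre- and post-chelation metals to a separate SAP for the metals core laboratory, which is not among the documents. SAP section 3.4 lists tertiles of blood lead and urine cadmium as subgroups.

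**The concern.** Benefit is a difference between what happens with chelation and what would have happened without it. Comparing treated patients who end low with treated patients who end high contains no such difference.

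The level a patient reaches carries the level that patient started with. If lead and cadmium raise cardiovascular risk, as the protocol holds, patients who end low include many who started low and were at lower risk before the first infusion. Two further routes are possible. The edetate dose is scaled to creatinine clearance (section 5.1), so attained level may partly reflect renal function. Patients who stop infusions are still asked to return for sampling (section 6.2.3), so it may also reflect adherence.

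The objective asks about depletion, whereas an unadjusted attained level is largely a measure of starting burden. The landmark is also not a single time: "if a patient has not completed the infusions by 1 year, they should continue trying to get the patient to clinic".

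At stake is the mechanistic claim. A low-versus-high difference within the chelation arm could be read as evidence that metal removal produces benefit. It could also feed the protocol's further question of whether metal levels should guide the number of sessions.

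**Working it through.** **Scale check against the plan's own figure.** The plan gives no figure for the landmark analysis, so its event calculation was reproduced first. Schoenfeld: D = 4(1.960 + 1.036)² / (ln 0.70)² = 4 × 8.978 / 0.1272 = 282.3, or 283 rounded up, against 282 in Protocol Table 3. All 18 cells of that table reproduce to within one event.

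**Inputs from the documents.** 1000 patients, 1:1 for chelation; 8.8% per patient-year (SAP Appendix I, projected scenario); 5% dropout per year (Protocol 9.2); follow-up 2.5 to 5 years (SAP 1.2 and 1.1), taken as uniform.

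**Assumptions.** Baseline log level is standard normal. The prognostic hazard ratio per SD, h, is 1.0 to 1.5. Chelation lowers every level by 1 SD and has no effect on events. The level at 1 year is baseline minus 1 SD plus noise with SD 0.5. The landmark is at 1 year.

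**Hand calculation.** Attained level has SD √(1 + 0.25) = 1.118, and its regression slope to baseline is 1/1.25 = 0.8. The mean of an outer tertile of a normal variable lies 1.091 SD from the centre. Lowest and highest attained tertiles therefore differ in *baseline* level by 0.8 × 2 × 1.091 × 1.118 = 1.95 SD. The expected hazard ratio is about h^(−1.95): 0.83 at h = 1.1, 0.70 at 1.2, 0.60 at 1.3 and 0.45 at 1.5.

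**Simulation, 1000 trials per row.** Percentages in columns 2 and 3 are trials nominally significant in favour of low levels.

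| h per SD | Chelation arm, low vs high half | Chelation arm, lowest vs highest tertile | Placebo arm, same median split | Low-half chelation vs all placebo | Randomised arm × baseline-tertile ratio (rejections) |
|---|---|---|---|---|---|
| 1.0 | 0.99 (2.0%) | 0.99 (2.5%) | 1.00 | 0.99 | 1.00 (4.7%) |
| 1.1 | 0.86 (12%) | 0.81 (12%) | 0.86 | 0.92 | 1.01 (4.5%) |
| 1.2 | 0.78 (20%) | 0.71 (24%) | 0.76 | 0.87 | 1.00 (4.8%) |
| 1.3 | 0.69 (39%) | 0.60 (48%) | 0.69 | 0.82 | 0.99 (6.8%) |
| 1.5 | 0.56 (72%) | 0.46 (81%) | 0.56 | 0.72 | 1.00 (6.6%) |

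- The placebo arm, where nobody was chelated, shows practically the same gradient as the chelation arm. The gradient is therefore not a treatment effect.
- Setting low-level chelation patients against the whole placebo arm reduces the bias but does not remove it.
- The randomised interaction with baseline tertile, run on the same trials, is close to 1 with rejections near 5%.
- About 435 chelation patients and 84 to 87 of their events remain after the landmark. At h = 1.2 that is 86 of about 127 (254/2), so roughly a third of the arm's events are not used.
- The simulated trials had 249 to 255 events in all, fewer than the plan's 282. With more events, the significance percentages for h above 1 would be somewhat higher.

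**Effect of baseline adjustment.** With attained level as a continuous covariate and h = 1.2, the unadjusted term favoured low levels significantly in 33% of trials. With infusion-1 level added this fell to about 4%, no more than chance.

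**Does replacing attained level by change help?** Write m for attained level and z for infusion-1 level. Then b₁m + b₂z = b₁(m − z) + (b₁ + b₂)z. The metal coefficient b₁ is the same either way once z is in the model. The adjustment does the work, not the choice of variable.

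**The case against.** The strongest reply has four parts.

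1. **The landmark sentence is a hypothesis in parentheses, not a model.** The protocol says elsewhere that levels will be related to effects relative to placebo, and the detail may sit in the unseen metals SAP. This stands as a limit: baseline adjustment may be specified there. It does not change the protocol text, which names the placebo comparison in approach 1 and omits it in approach 2.

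2. **The valid analysis is already planned.** Approach 1, the interaction tests in Protocol 9.6 and the subgroups in SAP 3.4 provide it. This stands, and it makes the repair cheap.

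3. **The analysis is exploratory and is meant to explain a benefit already seen.** With an overall hazard ratio near 1 there would be nothing to explain. This lowers the stakes. It does not make a within-arm contrast a measure of benefit, and a low-level group doing better could still be presented as the patients who responded.

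4. **The size rests on assumptions.** This stands. The protocol gives no hazard ratio for metals.

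Some stronger readings that a reader might infer are not supported:

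- *That the analysis would show a false benefit whatever the facts.* It would do so only if metal level is prognostic; at h = 1.0 the hazard ratio is 0.99.
- *That approaches 1 and 2 contradict each other.* They are in tension, because low finishers tend to be low starters. Both can hold if depletion varies, since a high starter may end low.
- *That approach 3 is fitted in the chelation arm alone.* The text ties that phrase to the metal changes. The result to be explained is superiority over placebo.
- *That depletion is ignored.* Approach 3 and the paragraph after it both address patterns of metal change.

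**Conclusion.** The point holds in conditional form. As written, approach 2 estimates prognosis by attained metal level within one arm and reads it as benefit. On the protocol's own premise it would tend to favour low-level patients with chelation inert. For assumed prognostic hazard ratios of 1.1 to 1.5 per SD, the lowest versus highest tertile hazard ratio runs from about 0.81 to 0.46, nominally significant in about 12% to 81% of trials. With no prognostic association there is no bias.

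The prognostic strength, the 1 SD reduction and the noise SD are assumptions. The simulation does not model the renal and adherence routes, whose direction the documents do not settle. The matter is confined to an exploratory mechanistic claim and should be corrected before that claim is reported.

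**What to change.** In Protocol 9.6, approach 2:

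- Adjust the landmark model for the pre-infusion level of the same metal at infusion 1, and for age, sex, insulin use and baseline creatinine clearance. The metal term then reflects depletion, as item iv.b asks. Do not adjust for number of infusions, because that would remove part of the depletion under study.
- Start each patient's follow-up at the date of the infusion-40/1-year sample, among those event-free at that date. Samples follow infusion number and no separate 12-month draw is scheduled, so a fixed 12-month landmark would not match the data.
- Report the result as a prognostic association within the chelation arm, and delete the claim of larger clinical benefits.
- Rest statements about who benefits on the randomised chelation-versus-placebo interaction with pre-infusion blood lead and urine cadmium at infusion 1. Post-infusion urine is itself changed by active treatment: section 2.2 reports a mean 3,926% rise in urinary lead after one infusion.
- Align the separate metals SAP.

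**Cost.** This is wording and analysis only; infusion-1 and infusion-40 samples are already scheduled. The mechanistic claim becomes weaker and the estimate less precise. Under the working assumptions with 86 events, the standard error of the log hazard ratio per unit of metal rises from about 1/(1.118 × √86) = 0.096 to 1/(0.5 × √86) = 0.216. Adjustment also does not make the association causal, and measurement error in the infusion-1 level would leave some confounding.
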